**2. LIST OF ABBREVIATIONS**

Term	Definition / description
AE	Adverse Event
ALT	Alanine Aminotransferase
Anti-VEGF	Anti-vascular endothelial growth factor
AST	Aspartate Transaminase
BNP	B-type natriuretic peptide
BRPM	Blinded Report Planning Meeting
CTC	Common Terminology Criteria
CTP	Clinical Trial Protocol
CPET	Cardiopulmonary Exercise Test
CRF	Case Report Form
DMG	Dictionary Maintenance Group
ECG	Electrocardiogram
FAS	Full Analysis Set
GERD	Gastroesophageal Reflux Disease
HRCT	High-resolution computed tomography
ICH	International Conference On Harmonisation
ILD	Interstitial lung disease
IPF	Idiopathic Pulmonary Fibrosis.
MedDRA	Medical Dictionary For Regulatory Activities
NOAC	Novel Oral Anticoagulant
NSAID	Nonsteroidal anti-inflammatory drugs
NTproBNP	N-terminal pro b-type natriuretic peptide
PT	Preferred Term
PV	Protocol Violation
SEAP	Statistical and Epidemiological Analysis Plan
SD	Standard Deviation
TSAP	Trial Statistical Analysis Plan

### **3. INTRODUCTION**

“As per ICH E9, the purpose of this document is to provide a more technical and detailed elaboration of the principal features of the analysis described in the protocol, and to include detailed procedures for executing the statistical analysis of the primary and secondary variables and other data in order to support future publications based on IPF patients.

This TSAP assumes familiarity with the Clinical Trial Protocol (CTP), including Protocol Amendments. In particular, the TSAP is based on the planned analysis specification as written in CTP Section 9.8 “Data Analysis”. Therefore, TSAP readers may consult the CTP for more background information on the study, e.g., on study objectives, study design and population, treatments, definition of measurements and variables, planning of sample size, randomization”.

#### **4. CHANGES IN THE PLANNED ANALYSIS OF THE STUDY**

As described in the study protocol only descriptive analysis will be applied for the purpose of the present study. Further to the summary tables of frequencies and measures of central tendency, Kaplan Meier curves will be produced to illustrate the survival distribution of patients in the study.

Analysis of the baseline characteristics was decided to be performed when all subjects had entered the trial.

## **5. ENDPOINTS(S)**

### **5.1 PRIMARY ENDPOINT(S)**

The main objective of this IPF registry is to gain further knowledge on the characteristics, management, progression and outcomes of patients with IPF as treated under real-world, clinical practice conditions in Greece.

More specifically, this registry is going to:

- Provide a comprehensive clinical picture for IPF
- Track access to health care and cost of caring for IPF patients over time
- Examine the implementation of treatment guidelines, used on patients diagnosed with IPF, according to the existing diagnosis guidelines
- Characterize patients on different treatments.

Endpoints are targeting the description of the following:

- Demographic data including age, gender and race, employment status and insurance status.
- Change from baseline in vital signs as measured at 3,6,12,18 and 24 months following to the baseline visit.
- Vital Status.
- Cardiopulmonary exercise testing (6-minute walk distance and CPET, if performed)
- Change from baseline in 6-minute walk distance VO2max (CPET) as measured at 3,6,12,18 and 24 months following to the baseline visit.
- IPF risk factors as measured at baseline visit: (cigarette smoking including pack years, alcohol and substance abuse, environmental and occupational exposure, exposure to drugs associated with IPF, exposure to viral infection possibly related to IPF, gastro - oesophageal reflux, genetic factors - family history).
- Description of the comorbidities throughout the trial.
- Risk of bleeding and thrombosis as stated in the CRF.
- Description of the newly diagnosed patients of acute respiratory worsening, exacerbations, and hospitalization due to any cause and due to IPF.
- Description of the intensity of treatment, frequencies and resource utilization for pharmaco-economic analyses.
- Description of methods and procedures used in the diagnosis of IPF and time since diagnosis.
- Description of IPF symptoms (dyspnea, cough, weight loss, fatigue, dizziness, chest pain, anxiety, clubbing, bibasilar crackles)

- Description of autoimmune biomarker.
- Description of lung function and/or exercise capacity.
- Description of IPF treatment modalities.
- Description of Physician's clinical rating of the probable course of IPF (stable, slow or rapid progression).
- Description of Clinical events and hospitalizations especially due to: (acute) respiratory worsening, including pneumonia, exacerbations of IPF, occurrence of pulmonary or cardiovascular complications, pulmonary rehabilitation, pulmonary embolism, pneumothorax, or cardiac failure.

## **5.2 SECONDARY ENDPOINT(S)**

### **5.2.1 Key secondary endpoint(s)**

[figure not shown]
Not applicable. No key secondary endpoints have been specified in the protocol.

### **5.2.2 Secondary endpoint(s)**

As secondary objective is to document in details the concomitant medication of specific drugs. Therefore, as secondary endpoints the drug name, dosage, duration of administration of each of the following drugs and their combinations will be summarized.

- Steroids
- Immunomodulators (azathioprine, cyclophosphamide, cyclosporine A, mycophenolate mofetil etc)
- N-Acetylcysteine
- Pirfenidone
- Nintedanib
- Anticoagulants
- Vit-K antagonist
- Heparin
- Antiplatelet therapy (if yes it will be specified if high dose antiplatelet therapy)
- Aspirin (if yes it will be specified if used as antiplatelet)
- GERD medication
- PDE-5 inhibitor (sildenafil, tadalafil)
- Endothelin receptor antagonist (bosentan, ambrisentan, macitentan)
- Long term oxygen therapy
- Listed for lung transplantation
- NSAIDs, other than aspirin
- Hormone replacement therapy
- Hormonal contraceptives
- Anti-VEGF drugs

- NOAC
- Other (specify).

## **6. GENERAL ANALYSIS DEFINITIONS**

### **6.1 TREATMENT(S)**

This is a non-international study and no treatment arms are considered for this trial. The subjects can receive treatment according to the standard practice for the IPF management.

### **6.2 IMPORTANT PROTOCOL VIOLATIONS**

Important PVs are those that can potentially influence the primary outcome measure for the respective subjects in a way that is neither negligible nor in accordance with the study objectives. All study inclusion/exclusion criteria are of equal importance.

#### *Inclusion Criteria*

- Newly diagnosed (less than 6 months) or patients previously diagnosed with IPF (more than 6 months prior to baseline visit), based upon the consensus statement jointly issued by ATS/ERS/JRS/ALAT in 2011 (see Annexes 6 and 7 on HRCT and histological criteria in Annex 6).
- Exclusion of other known causes of ILD (e.g., domestic and occupational environmental exposures, connective tissue disease, and drug toxicity)
- Evaluation of IPF with HRCT or combinations of HRCT and surgical lung biopsy, if available
- Age  $\geq 40$  years old at the time of inclusion
- Written informed consent for participation in the registry
- Patients that can be further followed up by the investigator, during the scheduled study period

[figure not shown]
#### *Exclusion Criteria*

- Expected lung transplantation within the following 6 months
- Participation in clinical trials

### **6.3 SUBJECT SETS ANALYSED**

The statistical analysis of the study will be based on the Full Analysis Set (FAS).

FAS is comprised of all subjects enrolled in the study with at least one measurement of the primary endpoint during the trial. This population will be used to run any statistics of the study. As there is no BI medication or product given for this study, there is not going to be any Treated Set. Therefore, any safety analysis will be performed also in the FAS.

## **6.5 POOLING OF CENTRES**

This section is not applicable because no statistical modelling will be employed.

## **6.6 HANDLING OF MISSING DATA AND OUTLIERS**

No imputation technique to fill in any missing values will be performed. Accordingly the Last Observation Carried Forward technique will not be applied.

Missing values will be differentiated from negative answers.

Summary statistics will be performed only on subjects with available information (unknown data will not account in the total population for each specific variable).

For missing or incomplete AE dates or drug administration dates, or other significant dates, the BI internal procedures and guidelines will be employed.

Missing dates related to AE events will not be imputed since no analysis based on duration of AEs or time to event will be employed:

Missing dates related to deaths will be handled according to BI standards and therefore, no subjects with incomplete date of death will be included in the time to event analysis.

Regarding outliers, the distributional properties should be examined by PP and/or QQ plots in conjunction with the summary statistics of mean/median/SD. Should the distributional properties of a variable indicate the existence of outliers, then the values will not be neglected from the analysis, but the variance will be reduced following the logarithmic transformation. Any implausible data will be treated separately and it will be judged based on case by case basis.

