## **7.4 NATURAL COURSE**

Data on the natural course of IPF are from retrospective and a few prospective studies, including the placebo arms of clinical trials (limited to short observation periods and by in/exclusion criteria). The previously reported median survival time of 2-3 years from the time of diagnosis could be an underestimate, at least when accounting for patients with preserved lung function. Notably, the natural course is unpredictable for a given patient at the time of diagnosis, while the majority of patients experience steady worsening (slow progression), others remain stable, or have rapid progression of disease [\[10-11\]](#). Acute respiratory worsening either due to secondary complications (e.g. pneumonia, pulmonary embolism, pneumothorax or cardiac failure) or due to unknown reasons (in this case the term acute exacerbation is used) are suggested to occur in about 5-10% annually [\[1\]](#). A recent retrospective review of 461 patients with IPF has found that the 1- and 3-year incidences of acute exacerbations were 14.2% and 20.7%, respectively [\[12\]](#).

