## **9.6 STUDY SIZE**

This observational study will be analyzed using descriptive statistics following standard statistical and epidemiological methods. Approximately 300 patients are expected to be included in the study in a consecutive manner between April 2017 and April 2019 from the participating sites according to the feasibility procedure of the sites.

The number of included patients as well as the duration of the study is not defined by a formal sample size and power calculation, but is based mainly on the availability of eligible IPF patients as well as patient population in the selected sites.

[Table 2](#) describes the expected precision for the description of a proportion, according to different sample sizes. Note that within Table 2 the first interval relates to an asymptotic 95% confidence interval and the second interval relates to an exact 95% confidence interval (i.e. The Clopper-Pearson interval).

Table 2. Precision of estimates for binary parameters

(Sub) group size	Proportion				
	50%	40%	30%	20%	10%
50	(36.14%, 63.86%)	(26.42%, 53.58%)	(17.30%, 42.70%)	(8.91%, 31.09%)	(1.68%, 18.32%)
	(35.53%, 64.47%)	(26.41%, 54.82%)	(17.86%, 44.61%)	(10.03%, 33.72%)	(3.33%, 21.81%)
100	(40.20%, 59.80%)	(30.40%, 49.60%)	(21.02%, 38.98%)	(12.16%, 27.84%)	(4.12%, 15.88%)
	(39.83%, 60.17%)	(30.33%, 50.28%)	(21.24%, 39.98%)	(12.67%, 29.18%)	(4.90%, 17.62%)
200	(43.07%, 56.93%)	(33.21%, 46.79%)	(23.65%, 36.35%)	(14.46%, 25.54%)	(5.84%, 14.16%)
	(42.87%, 57.13%)	(33.15%, 47.15%)	(23.74%, 36.86%)	(14.69%, 26.22%)	(6.22%, 15.02%)
300	(44.34%, 55.66%)	(34.46%, 45.54%)	(24.81%, 35.19%)	(15.47%, 24.53%)	(6.61%, 13.39%)
	(44.20%, 55.80%)	(34.41%, 45.79%)	(24.87%, 35.53%)	(15.62%, 24.98%)	(6.85%, 13.97%)

For continuous endpoints, precision of estimates will depend on parameter specific assumptions on mean and standard deviation. A generic display as given for binary endpoints is therefore less appropriate.

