## **9.10        LIMITATIONS OF THE RESEARCH METHODS**

The basic limitations of the study relate to the general limitations that concern non - interventional studies. Since this study is a non - interventional study, it could be possible that different parameters which were not assessed and thus remain unknown, might lead to overestimating/underestimating/non-detection of differences of specific patients' characteristics. Selection bias on the patient level will be minimized by consecutive enrollment. Survival in IPF cohort studies is affected by the clinical characteristics and the related baseline patient conditions, as well as by the time interval between the diagnosis and the inclusion of the patient in the protocol. Patients that have been long diagnosed (at least more than 6 months before entering the study) with IPF and are included in the registry may be more likely to have a relatively more stable disease and/or better response in IPF management compared to the newly diagnosed patients; however, given the disease progression they will be in different disease stages. In this registry it will be possible to differentiate based on disease duration.

In case patient is lost to follow up, every effort will be made to contact the patient, keep him/her involved and if possible inquire about the reason of loss to follow-up. In order to assess the effect of loss to follow-up, percentages of dropouts will be summarized and patients will be characterized and compared to the remaining patients.

No re-evaluation of patients in this study is initially foreseen, something, that can lead to the conclusion that patients with overlapping diagnoses (like fibrosing interstitial pneumonia of unknown cause) have been included in the study, thus depicting the difficulties in differential diagnosis in clinical practice. However, given the fact that the participating sites are reference centers for IPF, and considering the eligibility criteria that apply for this study, the expected bias might be low.

The study is going to provide evidence regarding the situation in the IPF reference centers which are University Pulmonology Clinics and Pulmonology Clinics at Hospitals of Public Setting that follow up about 70%-80% of IPF patients in Greece.

Given the small numbers and the heterogeneous population no comparisons and causal associations can be assessed.

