## **7. PLANNED ANALYSIS**

Continuous variables will be listed as mean value with standard deviation (SD) and median, along with minimum and maximum values (depending on the underlying distribution). The minimum and maximum values will have the precision of the data reported; mean, median values will have one additional decimal, whereas SD will have two additional decimals.

Categorical values will be listed as absolute and relative frequencies. Tabulations of frequencies for categorical data will include all possible categories and will display the number of observations in a category as well as the percentage (%) relative to the respective group (unless otherwise specified, all subjects in the respective subject set whether they have non-missing values or not). The precision for percentages should be one decimal point, unless the denominator is smaller than 100 (in all treatment columns), in which case percentages are given in integer numbers.

As soon as all patients are recruited and have the baseline visit recorded, then this visit will be analyzed. The information to be reported is shown at the corresponding revised display plan of the study, dated 24 April 2020.

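### By-visit tables rest on two conflicting denominators, and neither shows death, transplant or loss, so later visits can look more stable than the cohort is

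*SAP*

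**What the plan says.** SAP 6.6 states "Summary statistics will be performed only on subjects with available information", leaves unknown data out of the total for the variable concerned, and adds "No imputation technique to fill in any missing values will be performed". It asks that missing values be kept apart from negative answers. It gives no separate rule for a visit that does not exist because the patient has died, been transplanted or left.

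SAP 7 sets the base for categorical percentages differently: "unless otherwise specified, all subjects in the respective subject set whether they have non-missing values or not".

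SAP 5.1 lists the variables affected, among them the physician's "clinical rating of the probable course of IPF (stable, slow or rapid progression"), symptoms, treatment modalities and lung function. Change from baseline is planned for vital signs, 6-minute walk and VO2max (5.1, 7.8.3) and laboratory data (7.8.2). Lung function is only to be described.

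Deaths appear elsewhere: SAP 4 adds Kaplan-Meier curves and SAP 5.1 lists vital status.

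Protocol 9.4 ends follow-up at death, transplant or withdrawal of consent. It also censors a patient who, after a telephone visit, cannot come to the next one in person. On loss to follow-up, Protocol 9.10 promises that "percentages of dropouts will be summarized and patients will be characterized and compared to the remaining patients". The SAP text available has no section that does this, and SAP 4, which lists changes to the planned analysis, does not say it was dropped.

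**The concern.** Progression and outcomes over two years are part of the main objective. If the patients who leave the tables are mostly those doing worst, the month-24 column of a status table and the month-24 mean of a raw measurement describe a selected group. A table can then drift towards 'stable', or a mean can stay flat, while no patient has improved.

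The two denominator rules make this worse, because the same data give different percentages depending on which section the programmer follows. SAP 6.6 can be read as the exception that SAP 7 allows for, or SAP 7 can be read as the specific rule for categorical tables. Neither reading tells the reader how many patients at each visit are dead, transplanted, lost or simply without a form.

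**Working it through.** **1. The plan's own figure.** Protocol 9.6, Table 2, at n = 300 and 50%: 1.96 × √(0.5 × 0.5 / 300) = 5.66 points, giving 44.34% to 55.66%, as printed. The table reproduces. It concerns random error at a fixed n and says nothing about who remains.

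**2. How many may be gone by month 24.** No document gives this. Protocol 7.4 says: "The previously reported median survival time of 2-3 years from the time of diagnosis could be an underestimate". Assuming a constant hazard and a median counted from enrolment, mortality = 1 − 0.5^(24 / median in months). With 300 patients (Protocol 9.6: "Approximately 300 patients are expected to be included in the study in a consecutive manner"):

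| Median | Source | 24-month mortality | Alive of 300 |
|---|---|---|---|
| 2 years | Protocol 7.4 | 50.0% | 150 |
| 3 years | Protocol 7.4 | 37.0% | 189 |
| 4 years | assumed | 29.3% | 212 |
| 8 years | assumed | 15.9% | 252 |

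Transplants, withdrawals and missed tests come on top. The half-width in step 1 becomes 7.13 points at n = 189 and 8.00 at n = 150.

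**3. A status variable under each rule (all inputs assumed).** Baseline rating: 40% stable, 40% slow, 20% rapid. No patient changes rating. Mortality at 24 months: 25%, 45% and 75%.

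- Survivors as a share of all: 0.40 × 0.75 = 0.30; 0.40 × 0.55 = 0.22; 0.20 × 0.25 = 0.05; total 0.57, so 43% have died.
- SAP 6.6: 0.30/0.57 = 53% stable, 0.22/0.57 = 39% slow, 0.05/0.57 = 9% rapid.
- SAP 7: 30% stable, 22% slow, 5% rapid, 43% in no category.

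For lower mortality, multiply all three hazards by m, so that survival in each group is raised to the power m. With m = 0.5, survival is 0.866, 0.742 and 0.500; with m = 0.3 it is 0.917, 0.836 and 0.660.

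| m | Mortality | SAP 6.6: stable / slow / rapid | SAP 7: stable / slow / rapid / unlabelled |
|---|---|---|---|
| 1 | 43% | 53 / 39 / 9 | 30 / 22 / 5 / 43 |
| 0.5 | 26% | 47 / 40 / 13 | 35 / 30 / 10 / 26 |
| 0.3 | 17% | 44 / 40 / 16 | 37 / 33 / 13 / 17 |

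If mortality were 43% in every group, SAP 6.6 would give 0.40 × 0.57 / 0.57 = 40% stable: no distortion.

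**4. A continuous variable (simulation, all inputs assumed).** Baseline FVC 78% predicted, SD 17; mean decline 3 or 6 points a year; nobody improves. The hazard ratio for death is 1.49 per 10 points lower and 1.65 per SD faster decline. The between-patient spread of decline is also assumed, so only direction and rough size should be read. Month-24 results, survivors against everyone:

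| Mortality | Decline per year | Raw mean | Change from baseline |
|---|---|---|---|
| 25% | 3 | 75.7 v 72.1 | −5.2 v −6.0 |
| 37% | 3 | 77.5 v 72.0 | −4.8 v −6.0 |
| 37% | 6 | 73.0 v 66.0 | −9.3 v −12.1 |
| 50% | 3 | 79.7 v 72.0 | −4.5 v −6.0 |

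At 37% mortality and 3 points a year the raw mean is almost flat from 78, while the change from baseline keeps 80% of the decline (4.8/6.0). The strongest attenuation of change in any run was −7.9 against −12.0, about one third (hazard ratios 1.82 and 2.23, 50% mortality). With both hazard ratios at 1.0 there was no bias at any mortality.

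**The case against.** A reader might infer that every by-visit summary is limited to survivors. The documents do not support that: SAP 7 sets an all-subjects base for categorical percentages, and the rating, symptoms and oxygen use are categorical. In step 3 that rule already gives the 30 / 22 / 5 that a fixed denominator would give. It lacks only the label for the remaining 43%. This objection stands against the word 'every', but it leaves the conflict with SAP 6.6 and the missing label.

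A reader might also take 37-50% mortality as the plan's own figure. It is not. The median in Protocol 7.4 runs from diagnosis and is called a possible underestimate. The cohort also includes previously diagnosed patients, who Protocol 9.10 expects may be more stable, and excludes those expecting a transplant within six months.

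The mortality by rating in step 3 has no source, and holding ratings fixed is artificial. If 24% of surviving 'stable' patients were re-rated as worse, the table would show 0.30 × 0.76 / 0.57 = 40% stable, unchanged from baseline. So a rise in 'stable' is not assured. That table would still look level while surviving patients had worsened.

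The plan does disclose deaths, through Kaplan-Meier curves, vital status and incidence rates of events (Protocol 9.8.1). These do not show how many patients stand behind each by-visit percentage or mean. SAP 6.6 also leaves deaths with incomplete dates out of the time-to-event analysis.

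Finally, the dropout table may exist elsewhere. SAP section numbers jump from 6.3 to 6.5 and from 7.5.2 to 7.7, and the display plan was not available. SAP 7 cites that plan for the baseline visit, however. The fair statement is that the visible SAP does not carry over the dropout comparison.

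**Conclusion.** The point holds in this form. SAP 6.6 and SAP 7 give conflicting denominators, neither shows death, transplant or loss as a status, and the visible SAP does not implement the dropout comparison in Protocol 9.10. These three findings need no mortality assumption.

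Under SAP 6.6, later status percentages and raw means can look more stable than the cohort is. The size rests on assumptions: in the illustration 'stable' rises by 4 to 13 points at 17% to 43% mortality, and it depends on death being related to status. If it is not, the 6.6 figures are unbiased.

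It would go too far to say that the cohort will appear to stabilise, or that change-from-baseline tables go flat. Change lost between nothing and about a third in the runs made, and decline stayed visible in all of them. Nor do the documents invite reading a rise in 'stable' as a treatment effect, since Protocol 9.8.1 and 9.10 rule out treatment comparisons and causal conclusions.

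**What to change.** Reconcile SAP 6.6 with SAP 7, and add to 6.6 and 7.4 text along these lines:

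- By-visit tables of status variables use the baseline FAS as denominator, with separate rows for died, transplanted, lost/withdrawn and missing. The available-case percentage is shown alongside.
- Each by-visit table of a continuous variable or of change from baseline gives the same counts.
- Baseline characteristics are tabulated by end status (completed, died, transplanted, lost/withdrawn), which implements Protocol 9.10.

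The data are already planned: Protocol 9.3.2 records date, vital status and reason when a patient leaves, and 9.5 seeks survival status by telephone at the end of the study. No model or imputation is needed, so the plan stays descriptive. The cost is longer tables and one extra table.
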